9.3.2 Pharmacokinetic Statistical Methodology

[REDACTED]

CC1

[REDACTED]

[REDACTED]

[REDACTED]

[REDACTED]

CC1

[REDACTED]

CC1

[REDACTED]

[REDACTED]

[REDACTED]

PK parameters will be summarized using descriptive statistics.

9.4 Safety and Tolerability Assessments

9.4.1 Adverse events

Where changes in severity are recorded in the case report form, each separate severity of the AE will be reported in the listings, only the most severe will be used in the summary tables. A pre-existing condition is defined as an AE that starts before the participant has provided written informed consent and is ongoing at consent. A non-treatment emergent AE is defined as an AE which starts after informed consent but prior to dosing. A TEAE is defined as an AE which occurs postdose or which is present prior to dosing and becomes more severe postdose.

All AEs will be listed. All TEAEs will be summarized by treatment, severity and relationship to the investigational product. The frequency (the number of AEs, the number of participants experiencing an AE and the percentage of participants experiencing an AE) of TEAEs will be

summarized by treatment, Medical Dictionary for Regulatory Activities (MedDRA) version 23.1 system organ class and preferred term. The summary and frequency AE tables will be presented for all causalities and those considered related to the investigational product by the investigator. Any SAEs will be listed, including investigational-product related SAEs.

Discontinuations due to AEs will be listed.

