8.3.1. Time Period and Frequency for Collecting AE and SAE Information

All SAEs will be collected from the signing of the ICF until participation in the study has ended.

All AEs will be collected from the start of intervention until the follow-up visit.

Medical occurrences that begin before the start of study intervention but after signing of the ICF will be recorded on the Adverse Event eCRF.

Although all AEs after signing the ICF are recorded by the site in the eCRF/electronic data entry, SAE reporting to the sponsor begins after the participant has signed the ICF and has received study drug. However, if an SAE occurs after signing the ICF, but prior to receiving selpercatinib, it needs to be reported ONLY if it is considered reasonably possibly related to study procedures.

All SAEs will be recorded and reported to the sponsor or designee immediately and under no circumstance should this exceed 24 hours, as indicated in Appendix [10.3](#). The investigator will submit any updated SAE data to the sponsor within 24 hours of it being available.

Investigators are not obligated to actively seek AEs or SAEs after conclusion of the study participation. However, if the investigator learns of any SAE, including a death, at any time after a participant has been discharged from the study, and he/she considers the event to be reasonably related to the study intervention or study participation, the investigator must promptly notify the sponsor.

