5. STUDY DESIGN

This is a Phase 1, fixed-sequence, open-label study in healthy participants that will study dabigatran P-gp drug-drug interaction (DDI) with selpercatinib. The anticipated study duration for each individual participant is approximately 8 weeks.

Screening

All participants will be screened within 28 days prior to enrollment (Day 1).

Treatment and Assessment Period

Eligible participants will take part in 1 treatment period. Participants will be admitted to the clinical research unit (CRU) on Day -1 and remain resident in the CRU until discharge on Day 11. All participants will receive a single dose of 150 mg dabigatran on Day 1 and a single dose of 150 mg dabigatran coadministered with a single dose of 160 mg selpercatinib on Day 8. There will be a washout period of 7 days between dosing on Days 1 and 8.

PK blood sampling and safety assessments, including vital signs measurements, physical examinations, clinical laboratory tests, electrocardiograms (ECGs), and adverse event (AE) recording, will be performed.

Follow-up

Participants will return to the CRU for a safety follow-up visit within 14 to 17 days after the final dose.

The study schema is shown in [Figure 1](#).

[figure not shown]

Figure 1: J2G-MC-JZJV Study Schema

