6. TREATMENTS

The following is a list of the study treatment abbreviations that will be used in the TFLs. In AE outputs, treatment labels will also contain "(Day X)" information.

Day	Study Treatment Name	Treatment order in TFL
1	150 mg dabigatran	1
8	150 mg dabigatran + 160 mg selpercatinib	2

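### TEAEs are summarised by treatment over unequal periods (7 days versus 14 to 17 days, if events go to the most recent dose), which can inflate combination event counts by up to 2.0 to 2.4 times under a constant background rate and equal ascertainment

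*SAP*

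**What the plan says.** SAP Section 5 places the doses a week apart: "There will be a washout period of 7 days between dosing on Days 1 and 8". After the second dose, "Participants will return to the CRU for a safety follow-up visit within 14 to 17 days after the final dose". Participants "remain resident in the CRU until discharge on Day 11", so they are in the unit for the whole interval after dabigatran alone but for only about 3 days after the combination.

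Protocol Section 8.3.1 keeps collection open throughout: "All AEs will be collected from the start of intervention until the follow-up visit". The definition in SAP Section 9.4.1 sets no upper time limit: "A TEAE is defined as an AE which occurs postdose or which is present prior to dosing and becomes more severe postdose". The same section plans the tables: "All TEAEs will be summarized by treatment, severity and relationship to the investigational product". The frequency measures are "the number of AEs, the number of participants experiencing an AE and the percentage of participants experiencing an AE".

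SAP Section 6 lists two treatments, dabigatran on Day 1 and dabigatran plus selpercatinib on Day 8, and adds: "In AE outputs, treatment labels will also contain" the dosing day. Nothing in the SAP text says which treatment an event belongs to. Section 9.4.1 gives no common post-dose window and no person-time denominator. Section 9.4.8 plans no inferential safety analysis.

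**The concern.** Safety and tolerability of the combination is a secondary objective, and its endpoint is the number of TEAEs and SAEs (SAP Section 4). Protocol Section 4.2 chose the fixed sequence so that each participant serves as his or her own control for safety as well as PK, and Protocol Section 9.4.1.1 promises AE incidence for each treatment. Readers will therefore compare the two columns. With no model behind the table, they will take the raw figures at face value.

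A column that stays open two or more times as long will collect more background events even if selpercatinib adds none. The SAP already uses a matched period elsewhere: the vital-signs figures in Section 9.4.4 cover the first 24 hours after dosing in each treatment period. The TEAE tables have no such rule.

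**Working it through.** The documents give no AE rate or ratio for this point, so there is no planned figure to reproduce.

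**Inputs from the documents**
- Interval between doses: Day 8 − Day 1 = 7 days (SAP Section 5).
- Follow-up after the final dose: w = 14 to 17 days (SAP Section 5).
- In-unit time after the Day 8 dose: Day 11 − Day 8 = 3 days (SAP Section 5).
- Selpercatinib half-life: about 32 hours (Protocol Section 2.2).
- Completers: at least 30 (Protocol Section 1.1).

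**Assumptions**
- Each event is assigned to the most recent dose.
- The background rate is constant and is not given in the documents, so the 7-day participant risk p is varied.
- Ascertainment is equal in and out of the unit (relaxed below).

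**Number of events.** Ratio = w/7, so 14/7 = 2.00 to 17/7 = 2.43.

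**Percentage of participants.** Risk in the longer window = 1 − (1 − p)^(w/7). Dividing by p gives the ratio.

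| 7-day risk p | Risk over 14 to 17 days | Ratio | Expected participants of 30: 7 days, then 14 to 17 days |
|---|---|---|---|
| 10% | 19.0% to 22.6% | 1.90 to 2.26 | 3.0, then 5.7 to 6.8 |
| 20% | 36.0% to 41.8% | 1.80 to 2.09 | 6.0, then 10.8 to 12.6 |
| 30% | 51.0% to 57.9% | 1.70 to 1.93 | 9.0, then 15.3 to 17.4 |
| 50% | 75.0% to 81.4% | 1.50 to 1.63 | 15.0, then 22.5 to 24.4 |

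The percentage ratio is always below the event-count ratio, because a participant counts once.

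**If events cluster around dosing.** Let f be the share of 7-day events tied to the dose rather than to background. Event ratio = f + (1 − f) × w/7.
- f = 0.5: 0.5 + 0.5 × 2.00 = 1.50, to 0.5 + 0.5 × 2.43 = 1.71.
- f = 1: 1.0.

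**If outpatient events are under-reported.** Let a be ascertainment after discharge relative to the unit. Event ratio = [3 + a(w − 3)]/7.
- a = 0.5: (3 + 5.5)/7 = 1.21, to (3 + 7)/7 = 1.43.
- a = 0.25: (3 + 2.75)/7 = 0.82, to (3 + 3.5)/7 = 0.93.
- Ratio of 1: a = 4/(w − 3), which is 4/11 = 0.36 at 14 days and 4/14 = 0.29 at 17 days.

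**Equal 7-day windows.** Ratio = 7/7 = 1.0 under a constant rate and equal ascertainment. At a 32-hour half-life, 168 hours is 168/32 = 5.25 half-lives, leaving 2^(−5.25) = 2.6% of selpercatinib.

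**The case against.** A reader might infer that the combination will look 2.0 to 2.4 times worse with no drug effect, or that the table is biased against it by design. The documents do not support that. The range applies to event counts only, and it needs a constant rate, equal ascertainment and most-recent-dose assignment, none of which is stated. Most of the second window is outpatient, and the Schedule of Activities, as far as its layout can be read, shows no visit between discharge and follow-up. With weak outpatient reporting the ratio falls below 1, so neither size nor direction is fixed.

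Other points reduce the weight of the concern:
- The analysis is descriptive. The tables are repeated for events judged related to study drug, which should remove part of the background, and all AEs are listed.
- The detailed table layouts are in a separate shell document that is not available here.
- A participant who stops before Day 8 stays under safety evaluation (Protocol Section 7.1), so the dabigatran-alone period is not 7 days for everyone. Protocol Section 7.2 expects discontinuation to be uncommon.

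The case against replacing the main table with a 168-hour table also stands. The second window would still be about 3 in-unit and 4 outpatient days, against 7 in-unit days. Reading the Schedule of Activities together with the count of 5 clinical laboratory samples in Protocol Section 10.2.1, the first window appears to hold two scheduled laboratory checks (24 hours and Day 7) and the second only one (24 hours). The next check comes at follow-up. Protocol Section 2.3 names liver-function abnormalities and thrombocytopenia as events of special interest, and some could first be detected there. Plasma half-life does not rule out late-detected effects, and the fixed sequence leaves period effects mixed with treatment.

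None of this makes the two open-ended columns comparable. It limits the size that can be claimed, and it means an equal-window table should be added beside the full table.

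**Conclusion.** The concern holds in a conditional form. With most-recent-dose assignment, TEAEs are compared over 7 days versus 14 to 17 days, without a common window or person-time. Under a constant background rate and equal ascertainment, this can inflate combination event counts by up to 2.0 to 2.4 times. The percentage of participants is inflated about 1.9 to 2.3 times at a 7-day risk of 10%, and 1.7 to 1.9 times at 30%. Dose-clustered events or under-reporting after Day 11 make the distortion smaller or absent, and strong under-reporting could reverse it. The 7-day risks are illustrative.

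Only a descriptive secondary safety comparison is affected; the primary PK analysis is not. The change is still worth making, because the comparison serves a stated objective and the remedy needs no new data.

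**What to change.** In SAP Section 9.4.1:
1. State that each TEAE is assigned to the most recent dose before its onset or worsening.
2. Keep the full by-treatment TEAE table.
3. Add a by-treatment table limited to onset within 168 hours after each dose, with the Day 1 window closing at the Day 8 dose if that comes first. Show later events in a separate follow-up column. TEAEs per participant-day would be an alternative way to adjust for window length.
4. Footnote the unequal follow-up and the in-unit versus outpatient difference, which neither an equal window nor a person-time rate removes.

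The cost is a few sentences, one extra table in the shells and no new data. The downside is that late-detected events, such as laboratory abnormalities first seen at follow-up, fall outside the equal window. The full table must therefore remain.

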9.4.2 Concomitant medication

Concomitant medication will be coded using the World Health Organization (WHO) drug dictionary (Version WHODDSEP20B3), and listed.

9.4.3 Clinical laboratory parameters

Liver enzyme tests data (ALP, AST, ALT) will be summarized. All clinical chemistry, hematology, and urinalysis data will be listed. Additionally, clinical chemistry, hematology and urinalysis data outside the reference ranges will be listed and flagged on individual participant data listings.

9.4.4 Vital signs

Vital signs data will be summarized by treatment together with changes from baseline. Baseline is defined as Day 1 predose for the first dose, and Day 7 predose for the second dose. Figures of mean vital signs and mean changes from baseline profiles will be presented by treatment, for the first 24 hours after dosing in each treatment period.

Values for individual participants will be listed.

9.4.5 Electrocardiogram (ECG)

ECGs will be performed for safety monitoring purposes only and will not be presented. Any clinically significant findings from ECGs will be reported as an AE.

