9.4.1.2. Statistical Evaluation of Safety

Safety parameters that will be assessed include safety laboratory parameters, vital signs, and ECG parameters. The parameters will be listed and summarized using standard descriptive statistics. Additional analysis will be performed if warranted upon review of the data.

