9. STATISTICAL METHODOLOGY

9.1 General

Data listings will be provided for all data that are databased. Summary statistics and statistical analysis will only be presented for data where detailed in this SAP. For continuous data, summary statistics will include the arithmetic mean, arithmetic standard deviation (SD), median, minimum, maximum and N; for log-normal data (e.g. the PK parameters: AUCs and C_{max}) the geometric mean and geometric coefficient of variation will also be presented. For categorical data, frequency count and percentages will be presented. Data listings will be provided for all participants up to the point of withdrawal, with any participants excluded from the relevant

population highlighted. Summary statistics and statistical analyses will generally only be performed for participants included in the relevant analysis population. For the calculation of summary statistics and statistical analysis, unrounded data will be used.

Mean change from baseline is the mean of all individual participants' change from baseline values. Each individual change from baseline will be calculated by subtracting the individual participant's baseline value from the value at the timepoint. The individual participant's change from baseline values will be used to calculate the mean change from baseline using a SAS procedure such as Proc Univariate.

Data analysis will be performed using SAS® Version 9.4 or greater.

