11. CHANGES FROM THE PROTOCOL SPECIFIED STATISTICAL ANALYSES

There were no changes from the protocol specified statistical analyses.

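### The SAP drops the ECG listing and summary that the protocol specifies, and narrows the laboratory summary, while section 11 declares no change from the protocol

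*SAP*

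**What the plan says.** Protocol section 9.4.1.2 sets the scope: "Safety parameters that will be assessed include safety laboratory parameters, vital signs, and ECG parameters". The next sentence sets the presentation: "The parameters will be listed and summarized using standard descriptive statistics". It does not limit this to a subset of tests.

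The SAP treats the three families differently. Section 9.4.4 lists vital signs and summarizes them by treatment, with changes from baseline. Section 9.4.5 says: "ECGs will be performed for safety monitoring purposes only and will not be presented", and adds that clinically significant ECG findings are to be reported as adverse events. Section 9.4.3 says: "Liver enzyme tests data (ALP, AST, ALT) will be summarized", followed by "All clinical chemistry, hematology, and urinalysis data will be listed", with out-of-range values flagged.

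Two general rules in SAP section 9.1 bear on how these sections are read: "Data listings will be provided for all data that are databased" and "Summary statistics and statistical analysis will only be presented for data where detailed in this SAP". On departures from the protocol, SAP section 11 says: "There were no changes from the protocol specified statistical analyses".

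**The concern.** A whole family of protocol-specified safety output disappears between the two documents, and the section meant to record such departures says there were none. A report that follows the SAP would omit that output and repeat the statement that nothing changed.

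ECG is not an incidental measurement here. Protocol section 2.3 names QT prolongation among selpercatinib's common toxicities, section 7.1 sets QTc withdrawal criteria, and the schedule of activities places predose and 2-hour ECGs around dosing. Section 2.2 gives a median selpercatinib tmax of 2 hours. Reporting through adverse events passes on only what an investigator judges clinically significant. A shift too small to be significant in any one participant would leave no trace in the report.

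The laboratory gap is smaller. The protocol calls for summaries of the safety laboratory parameters, and the SAP provides them for three liver enzymes only. Total bilirubin, creatinine, platelets and the coagulation tests have none.

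**Working it through.** The plan gives no figure to reproduce. The check is a comparison of text, plus one count.

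**1. Promised against planned, by family**

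| Family | Protocol 9.4.1.2 | SAP listing | SAP summary |
|---|---|---|---|
| Vital signs | list and summarize | yes (9.4.4) | yes, by treatment (9.4.4) |
| Safety laboratory | list and summarize | yes (9.4.3, 9.4.7) | ALP, AST and ALT only (9.4.3) |
| ECG | list and summarize | none (9.4.5) | none (9.4.5) |

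Two of the three families fall short of the protocol: ECG on both counts, laboratory on the summary only.

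**2. Whether another SAP section restores the output**

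- Section 9.4.7 lists safety assessments that section 9.4 does not otherwise cover. ECG is covered, in 9.4.5, so 9.4.7 does not reach it.
- Section 9.1 confines summaries to data that the SAP details, so laboratory tests not named in 9.4.3 get none.
- Coagulation is not named in 9.4.3. It would still be listed, either as part of hematology or under 9.4.7, and under 9.4.6 where hepatic monitoring applies.
- The redacted SAP text lies in sample size (section 7) and PK inference (section 9.3.2), not in safety presentation.

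**3. Laboratory count, from protocol Appendix 10.2**

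- Hematology: 8 + 5 differential counts = 13.
- Coagulation: PT, aPTT, INR = 3.
- Routine chemistry, leaving out ethanol, drug, virology, pregnancy and FSH tests: 17.
- Total: 13 + 3 + 17 = 33 blood analytes.
- Summarized: ALP, AST, ALT = 3. This is 3/33 = 9.1% overall and 3/17 = 17.6% of chemistry, with 0 of 13 in hematology and 0 of 3 in coagulation.
- The 9 dipstick urinalysis items are left out. Including them gives 3/42 = 7.1%.

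**4. Whether the protocol version explains the difference**

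SAP section 3 says the SAP was developed from the protocol dated 21 December 2020. The protocol supplied includes amendment (a) of 03 March 2021. The amendment's change table touches ECG interpretation (8.2.3) and the laboratory list (10.2) but has no entry for section 9.4. This is good evidence that 9.4.1.2 read the same in December, though not proof.

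**5. SAP 9.1 against SAP 9.4.5**

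Section 9.1 promises a listing of every data item that is databased. Protocol section 8.2.3 has ECG recordings stored at the site, and neither document says whether the intervals are entered in the database. If they are, 9.1 and 9.4.5 conflict. If they are not, the two SAP sections agree with each other, and the conflict with the protocol remains.

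**The case against.** The best defence is that the SAP may do this. Its section 3 says that it supersedes the protocol's statistical considerations and promises to identify only substantial differences. Laboratory listings with flags are kept, safety is descriptive throughout, and the safety endpoints are adverse event counts. For the laboratory reduction this has force, because whether it is substantial is a matter of judgment. For ECG it is hard to sustain, since a full parameter family is removed. In neither case does it rescue section 11, which is unqualified.

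Three stronger readings are tempting, and the documents do not support them.

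- A reader might infer that QT effects will go wholly unreported. They will not. Protocol sections 7.1 and 8.2.3 and SAP 9.4.5 send clinically significant findings to adverse events. SAP 9.4.1 lists all adverse events, tabulates the treatment-emergent ones by treatment, and lists discontinuations due to adverse events.
- A reader might infer that creatinine or platelet changes can appear only in listings. Protocol section 8.2.4 requires clinically relevant laboratory changes to be recorded as adverse events, and Appendix 10.3.1 defines clinically significant abnormal results as such.
- A reader might infer that the SAP plainly contradicts itself between 9.1 and 9.4.5. That depends on whether ECG intervals are databased, which the documents do not say.

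It is also fair to say that the analyte percentage counts tests rather than safety information lost, and that protocol 9.4.1.2 does not ask for laboratory or ECG summaries by treatment. The own-control rationale in protocol section 4.2 makes such summaries useful but does not make them a requirement.

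**Conclusion.** The point holds, chiefly for ECG. The protocol specifies a listing and a descriptive summary of ECG parameters, the SAP plans neither, and the SAP's declaration of no change is wrong as written. The laboratory point is secondary: 30 of 33 blood analytes lose their descriptive summary but not their listing.

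The consequence is limited to descriptive safety reporting and to the accuracy of section 11. The primary PK endpoints and the TEAE and SAE counts do not change, and participants receive a single selpercatinib dose. It still deserves correction, because QT prolongation is a named toxicity and the protocol schedules ECGs around dosing.

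The conclusion assumes that section 9.4.1.2 of the December 2020 protocol matched the current text. The table and listing shells that accompany the SAP were not available either, although SAP 9.1 limits the summaries they could add.

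**What to change.** - Amend SAP 9.4.5 so that ECG parameters are listed and summarized with descriptive statistics.
- Extend the summaries in SAP 9.4.3 to the protocol's safety laboratory parameters.
- If either reduction is kept, rewrite SAP section 11 to declare it and give the reason.
- State in the SAP whether ECG intervals are databased, so that 9.1 and 9.4.5 can be read together.

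Presenting the added summaries by treatment, as SAP 9.4.4 does for vital signs, would be useful but is not required by the protocol.

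The cost is SAP wording and a few standard tables. The one real burden is that ECG intervals may have to be entered from site records. Correcting section 11 alone needs no new output, but it would leave the protocol's ECG presentation undone.
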